Study Population	All adult patients with arteriovenous access flow dysfunction in Hospital Kuala Lumpur and University Malaya Medical Centre during the period 1 July 2023 – 30 June 2024.
Study Design	A randomized controlled study. Selected subjects will be randomized into ultrasound-guided fistuloplasty and fluoroscopy-guided fistuloplasty groups in a ratio of 1:1
General Objective	To investigate patencies in patients with arteriovenous access flow dysfunction receiving ultrasound-guided fistuloplasty versus fluoroscopy-guided fistuloplasty at 6 months
Specific Objectives	
 To investigate patencies in patients with arteriovenous access flow dysfunction receiving ultrasound-guided fistuloplasty versus fluoroscopy-guided fistuloplasty at 6 months, To capture data regarding variables that may affect patency of arteriovenous access flow dysfunction post ultrasound-guided fistuloplasty versus fluoroscopy-guided fistuloplasty, To compare technical success in patients with arteriovenous access flow dysfunction receiving ultrasound-guided fistuloplasty versus fluoroscopy-guided fistuloplasty, and To compare complication rates in patients with arteriovenous access flow dysfunction receiving ultrasound-guided fistuloplasty versus fluoroscopy-guided fistuloplasty.
Study endpoints/outcomes	(a) Patency of arteriovenous fistula over a period of six months post fistuloplasty; (b) Resolution of symptoms; (c) Technical success; (d) Percentage increase in volume flow.
Sample Size	54 subjects.
Study Duration	1 July 2023 - 31 December 2024.

1. Background and Significance

Arteriovenous fistulas (AVF) are the vascular access of choice for hemodialysis patients. In the United States from August 2010 to August 2013, arteriovenous fistula (AVF) use increased from 63% to 68% and across 20 other countries in 2013, arteriovenous fistula (AVF) use ranged from 49% to 92%.¹ Patency and functionality of haemodialysis access influences survival and quality of life for patients with chronic renal failure. Progressive narrowing of the perianastomotic lumen or a more proximal part of venous circulation as a result of intimal proliferation is the main cause of failure of arteriovenous fistula. The use of Doppler sonography allows identification of more than 50% arteriovenous fistula stenosis, with 92% sensitivity and 84% specificity.² Percutaneous transluminal fistuloplasty is a well-established therapeutic option for patients with haemodialysis vascular access stenosis. It is conventionally guided and monitored radiographically, but this carries the risks of ionizing radiation exposure and of adverse reaction to contrast media and this is the usual practice in Hospital Kuala Lumpur and University Malay Medical Centre.

Recently, we have observed an increasing role of ultrasonography (USG) in imaging of arteriovenous fistula. Superficial location of arteriovenous fistula allows for simple and reliable visualization of vessels, guidewire, catheter, balloon, etc., with significant technical advantages including the ability to directly visualize puncture sites, stenosis, thrombus, spasm, and extravascular flow in real time. Recent studies showed that percutaneous transluminal fistuloplasty can be performed under only sonographic guidance without using a fluoroscopic machine and it is as effective as conventional percutaneous transluminal fistuloplasty as shown in Appendix 1. Since more than a decade of described ultrasound-guided fistuloplasty, many small series have been published till date, but most of them studied small number population and without direct head-to-head comparison with fluoroscopy-guided fistuloplasty as shown in Appendix 2. To overcome these limitations and further evaluate the efficacy of the procedure, we would like to compare patency of arteriovenous access flow dysfunction post ultrasound-guided fistuloplasty versus fluoroscopy-guided fistuloplasty.

We would like to research upon the efficacy of ultrasound-guided fistuloplasty as an alternative to fluoroscopy-guided fistuloplasty to prolong patency of patients with arteriovenous access flow dysfunction.

2. Objective

To determine the efficacy of ultrasound-guided fistuloplasty compared to fluoroscopy-guided fistuloplasty in patients with arteriovenous access flow dysfunction.

3. Methodology

Study design: Multicentre, randomized controlled trial.

Location: Hospital Kuala Lumpur and University Malaya Medical Centre.

Population: Vascular clinic patients in Kuala Lumpur Hospital and University Malaya Medical Centre.

1. Treatment group: Patients who underwent ultrasound-guided fistuloplasty for arteriovenous access flow dysfunction are assessed prospectively for a period of 6 months.
2. Control group: Patients who underwent fluoroscopy-guided fistuloplasty for arteriovenous access flow dysfunction are assessed prospectively for a period of 6 months.

Sampling method: Simple random sampling.

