3.3 Inclusion Criteria

NO.	INCLUSION CRITERIA	EVALUATION METHOD.
1	Patient able to comprehend English or Malay language.	Speak to patient.
2	Patient aged ≥ 18 years and ≤ 80 years.	Examine patient personal data.
3	Patient is willing to comply with protocol.	Ask the patient.
4	Native AVF that is able to provide prescribed dialysis consistently with 2 needles for $>2/3$ of dialysis sessions within 4 consecutive weeks.	Ask the patient & examine dialysis record.
5	Patient has a reasonable expectation of remaining on haemodialysis for 6 months.	Ask the patient.

6	Dampened thrill or pulsatile flow.	Palpate the arteriovenous fistula.
7	Volume flow (VF) <500 ml/min.	Ultrasound doppler measurement.
8	Severe stenosis (>50%) of arteriovenous (AV) access measured on color image and confirmed by peak systolic velocity (PSV) ratio of ≥ 3 in the inflow artery, anastomosis, or in the outflow vein.	Ultrasound doppler measurement.

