3.4 Exclusion Criteria

NO.	EXCLUSION CRITERIA	EVALUATION METHOD.
1	Prior history of fistuloplasty.	Ask the patient and examine hospital record.
2	Thrombosed or completely occluded fistula or outflow vein.	Palpate the arteriovenous fistula and by using ultrasound doppler.
3	Non-mature AVF.	Palpate the arteriovenous fistula and by using ultrasound doppler.
4	Arteriovenous grafts.	Ask the patient, examine hospital record and by using ultrasound doppler.
5	Suspected central vein stenosis/ cephalic arch stenosis - arm edema or Doppler detected suspicion of the same.	Ultrasound doppler measurement
6	Non consenting patient.	Ask the patient
7	Metastatic cancer or terminal medical condition.	Ask the patient and examine hospital record.
8	Limited life expectancy (<6 months).	Ask the patient and examine hospital record.
9	Blood coagulation disorders (haemophilia/ Von Willebrand disease/ clotting factor deficiencies/ liver disease).	Ask the patient and examine hospital record.
10	Connective tissue disease (rheumatoid arthritis/ lupus).	Ask the patient and examine hospital record.
11	Sepsis or active infection.	Ask the patient and examine for any signs of infection.
12	Planned access abandonment within 6 months (eg, peritoneal dialysis or transplant).	Ask the patient.
13	Pregnant women or women of childbearing potential who are not following an effective method of contraception.	Ask the patient and obtain urine pregnancy test.
14	Allergy or other known contraindication to iodinated media contrast.	Ask the patient and examine hospital record.
15	Patient enrolled in another access maintenance trial.	Ask the patient.

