3.6 Sample Size

Based on a power of 80% ($\beta=0.2$), alpha of 0.05, a response anticipated difference of 90% in ultrasound-guided fistuloplasty group and 52.4% in fluoroscopy-guided fistuloplasty group, the calculated sample size for each group is 22 patients. Allowing for 20% dropout, a final sample size of 27 per group will be used.

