3.8 Study Visits and Procedures

Follow-up will be done at two weeks, one month, three months and six months.

Assessment during follow-up includes:

- Resolution of symptoms (prolonged post dialysis bleeding or difficult access cannulation).
- Reduction of venous dialysis pressure to below predefined threshold values. (the acceptable value is less than 150mmHg)
- Measurement of the volume flow (the acceptable value is more than 500ml/min), flow characteristics (the acceptable characteristic is laminar flow) and diameter of the target lesion (the acceptable diameter is between 5-6mm) using duplex ultrasound.

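### Endpoint (d), percentage increase in volume flow, measures flow outcome inefficiently; 6-month flow adjusted for baseline makes better use of the same readings

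*Combined protocol and SAP*

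**What the plan says.** The synopsis (Study endpoints/outcomes) gives four endpoints, the last being "d) Percentage increase in volume flow". It does not recur among the outcomes in section 3.1, and no formula or visit is attached to it.

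Entry criterion 7 in section 3.3 is "Volume flow (VF) <500 ml/min". No lower limit in ml/min is set. The nearest thing to one is exclusion 2 in section 3.4, "Thrombosed or completely occluded fistula or outflow vein".

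Section 3.8 states "Follow-up will be done at two weeks, one month, three months and six months", and the assessments include "Measurement of the volume flow (the acceptable value is more than 500ml/min". Absolute flow is therefore read at entry and at four later visits. Section 3.1 also includes flow above 500 ml/min in its definition of technical success.

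Section 3.9 names a t-test for the primary objective and logistic regression for the secondary objective. It assigns no method to a continuous flow outcome and plans no adjustment for baseline flow.

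**The concern.** A percentage change from baseline is a ratio whose denominator here may be any positive value under 500 ml/min. The score cannot fall below -100% but has no ceiling, so the smallest denominators produce the largest scores. This has two consequences.

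- **Interpretation.** A high score need not mean that the fistula reached the flow that the plan calls acceptable.
- **Precision.** With 22 to 27 patients per arm, part of the difference between arms may reflect which arm happened to draw the lowest baselines.

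The trial already collects the readings for a more precise comparison.

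**Working it through.** **The plan's own figure.** The documents give no number for endpoint (d). The only planned size is for patency in section 3.6: "Based on a power of 80% ($\beta=0.2$), alpha of 0.05", with "90% in ultrasound-guided fistuloplasty group and 52.4% in fluoroscopy-guided fistuloplasty group". Using the two-sided pooled formula, with mean proportion (0.90 + 0.524)/2 = 0.712:

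n = [1.96 × √(2 × 0.712 × 0.288) + 0.8416 × √(0.90 × 0.10 + 0.524 × 0.476)]² / (0.90 − 0.524)² = (1.2552 + 0.4903)² / 0.1414 = 21.55, rounded up to 22.

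This agrees with "the calculated sample size for each group is 22 patients". The stated 27 is 22 × 1.2 = 26.4, rounded up. The figure of 22 per arm is used below only as the evaluable number.

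**Step 1: ranking.** Score = 100 × (follow-up − baseline) / baseline. All baselines below are eligible.

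| Baseline | Follow-up | Score | Above 500? |
|---|---|---|---|
| 100 | 400 | +300% | no |
| 450 | 550 | +22% | yes |
| 150 | 450 | +200% | no |
| 450 | 900 | +100% | yes |

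**Step 2: weight of low baselines.** The same follow-up flow of 600 ml/min scores +500% from 100, +200% from 200, +100% from 300, +50% from 400 and +20% from 499. In an arm of 22, the patient who started at 100 adds 500/22 = 22.7 points to the arm mean. The patient who started at 400 adds 50/22 = 2.3.

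**Step 3: power.** The documents give no flow mean, SD or correlation, so these inputs are assumptions: 22 per arm; baseline truncated below 500 ml/min (median about 310, 5th to 95th percentile roughly 160-170 to 470); 6-month log-SD 0.40; true flow ratio 1.4. Results span several runs with similar inputs.

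| Baseline/6-month correlation | Percentage increase, t-test | Log flow adjusted for log baseline |
|---|---|---|
| 0.2 | 57-61% | 78-79% |
| 0.4 | 72-75% | 83-84% |
| 0.6 | 88-90% | 91-93% |
| 0.8 | 99% | 99% |

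Type I error was near 5% for both methods.

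**Step 4: other flow models.** Here the true shift was 0.87 SD, again with 22 per arm. Additive means follow-up flow of mean 700, SD 200 ml/min; multiplicative means follow-up proportional to baseline, with log-SD 0.4. Power is for the percentage t-test versus the log-scale adjusted model.

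| Baseline range | Additive, r = 0 | r = 0.3 | r = 0.6 | Multiplicative |
|---|---|---|---|---|
| 100-499 | 25% v 77% | 34% v 81% | 50% v 92% | 78% v 80% |
| 200-499 | 47% v 77% | 64% v 82% | 85% v 91% | 77% v 79% |
| 300-499 | 67% v 77% | 80% v 81% | 94% v 93% | 79% v 80% |

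In the additive case with no treatment effect, the rank correlation between baseline and score was -0.79 to -0.67, -0.64 to -0.29 and -0.44 to +0.12 for the three ranges. A fistula below the cut-off outscored one above it in 18-41%, 9-15% and 3-4% of such pairs. In the multiplicative case the correlation was 0.

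**Step 5: source of the loss.** Since log(1 + score/100) = log follow-up − log baseline, the log of the ratio adjusted for log baseline gives the same arm effect and p-value as log follow-up adjusted for log baseline. In one Step 3 run, power at correlations 0.2/0.4/0.6 was 61/75/90% for the unadjusted score, 73/79/90% once adjusted for log baseline, and 78/83/91% on the adjusted log scale. The loss comes from the raw scale and the missing adjustment.

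None of these runs represents a thrombosed access, because the log model needs positive flow.

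**The case against.** The strongest reply is that improvement and attained level are different questions. Sections 3.1 and 3.8 already assess absolute flow against 500 ml/min, so a fistula at 400 ml/min fails that check whatever its percentage gain. This stands. A reader might infer that endpoint (d) contradicts the protocol's cut-off, but the documents do not support that: (d) sits beside the cut-off and does not override it.

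Second, the t-test used as comparator is not in the plan for (d), which has no stated analysis. This also stands, so the power figures are conditional on that choice. Step 5 shows too that the loss can be cured by adjustment and a log scale while keeping the ratio, so it would be wrong to call the ratio irreparable whatever the test.

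Third, the gain rests on assumed flows. It is absent at correlation 0.8, absent with baselines of 300-499 and r = 0.6, and small if treatment multiplies flow. In that last case the score is unrelated to baseline, so the dependence on baseline is not universal.

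Fourth, zero flow cannot be logged, whereas percentage increase gives it -100%. A log model used alone would drop thrombosed accesses. This is correct and shapes the fix.

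The replies leave untouched the arithmetic of Steps 1 and 2, and the fact that adjustment for baseline uses data already collected.

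**Conclusion.** The point holds as an efficiency and interpretability weakness in a non-primary endpoint. With the Step 3 assumptions, the adjusted log analysis gains 17 to 21 power points at correlation 0.2, 8 to 12 at 0.4 and 1 to 5 at 0.6 (differences within runs), and none at 0.8. The ranking and weighting results need no distributional assumption; the power results do.

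A reader might go further and infer bias or an inflated false-positive rate. Neither follows: allocation is randomised, imbalance in baseline flow is chance, and type I error stayed near 5% throughout. The sample size was set on patency and is unaffected. The priority is low, but the change is nearly free.

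**What to change.** In the synopsis and section 3.9, define the flow endpoint as volume flow at 6 months, compared between arms with adjustment for baseline flow (the inclusion 7 reading). Six months is a choice, consistent with the general objective and the visit schedule.

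- **Main test:** a rank-based analysis of covariance, with a thrombosed access given the lowest rank so that it is not dropped.
- **Supporting estimate:** the ratio of geometric means from log flow adjusted for log baseline among patent accesses, labelled as conditional on patency.
- **Alongside:** the share above 500 ml/min, counting thrombosed accesses as not reaching it.
- **Descriptive only:** percentage increase.

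The cost is about one line in each of the two places. The readings are already scheduled, the analysis runs in SPSS, and nothing changes for patients. The downside is that a rank test gives a less direct effect size and slightly less power than the log model when no access thromboses. The power figures above are for the log model; the rank version was not simulated.

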3.1 Study Type and Design

This is an experimental study employing a prospective randomized controlled trial.

The primary outcome would be to compare the patency of arteriovenous fistula at one, three and six months.

Secondary outcomes shall include:

- To capture data regarding variables that may affect patency of arteriovenous access flow dysfunction post ultrasound-guided fistuloplasty versus fluoroscopy-guided fistuloplasty,
- To compare technical success (defined as clinical palpable thrill, radiographic finding of less than 30% recoil and ultrasonographic finding of continuous segment of dilated vein to 5-6mm and continuous flow rate of more than 500ml/min) in patients with arteriovenous access flow dysfunction receiving ultrasound-guided fistuloplasty versus fluoroscopy-guided fistuloplasty and
- To compare complication rates in patients with arteriovenous access flow dysfunction receiving ultrasound-guided fistuloplasty versus fluoroscopy-guided fistuloplasty

Patients are randomized using simple randomization method. Treatment plans are divided equally between ultrasound-guided fistuloplasty and fluoroscopy-guided fistuloplasty. An application “sealedenvelope.com” is used for this purpose. The application does this via a built in random number generator.

After assessing for eligibility, patients will be randomized equally with a ratio 1:1 to ultrasound-guided fistuloplasty group and fluoroscopy-guided fistuloplasty group.

Both interventions will be done in operation theatre to maintain sterility. After cleaning and draping the area of interest, local anaesthesia is given to the puncture site. A puncture needle is used to gain access to the arteriovenous fistula followed by a guide wire. Then, a sheath with an appropriate size is placed and a balloon catheter of adequate size is inserted over the guide wire and inflated for 2 minutes. Ultrasound is used in the subject group to monitor technical success. On table visualization of continuous segment of dilated vein to 5-6mm and continuous flow rate of more than 500ml/min signifies the end points of the procedure.

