3.5 Withdrawal Criteria

Subjects can choose to withdraw at any time. Subjects may be withdrawn if the investigator deems that it is detrimental or risky for the subject to continue. All withdrawn subjects should attend the final study visit. Withdrawn subjects will not be replaced.

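### Groups and six-month assessment are defined by having undergone fistuloplasty, so patients randomised but never dilated have no secured follow-up and no outcome rule

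*Combined protocol and SAP*

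**What the plan says.** Section 3 (Methodology) defines the treatment group as "Patients who underwent ultrasound-guided fistuloplasty for arteriovenous access flow dysfunction are assessed prospectively for a period of 6 months" and the control group as "Patients who underwent fluoroscopy-guided fistuloplasty for arteriovenous access flow dysfunction are assessed prospectively for a period of 6 months". Membership of a group and the six-month assessment both follow from having had the procedure.

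Section 3.1 places allocation earlier: "After assessing for eligibility, patients will be randomized equally with a ratio 1:1". Puncture, wire, sheath and balloon come after that.

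The synopsis lists the first endpoint as "Patency of arteriovenous fistula over a period of six months post fistuloplasty", so the clock starts at the procedure. Section 3.1 makes patency at one, three and six months the primary outcome and compares technical success among patients receiving each procedure. Section 3.9 names one analysis basis, per protocol.

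Other text is more general. Section 3.8 says "Follow-up will be done at two weeks, one month, three months and six months", without limiting this to treated patients. Section 3.7 gives each subject six months of participation. Section 3.5 says "All withdrawn subjects should attend the final study visit" and does not replace those who withdraw.

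**The concern.** Between allocation and balloon inflation a patient can drop out of the treated set: the fistula may thrombose while the patient waits for theatre, the lesion may not be crossed, or the procedure may not go ahead for another reason. These patients entered with flow below 500 ml/min and a stenosis above 50% (section 3.3), so many would probably be read as not patent. If they are not followed or counted, each arm's patency describes those who reached dilatation, and the protection given by randomisation is lost after allocation.

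Equal loss in both arms does little harm to the comparison; unequal loss biases it. Unequal loss is plausible here. One arm is guided by ultrasound and the other by fluoroscopy. At University Malaya Medical Centre a vascular surgeon performs the ultrasound procedures, while an interventional radiologist, not yet named, performs the fluoroscopic ones. Waiting times and the chance of a completed procedure could therefore differ.

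This is partly a data-collection problem. A later switch to analysis by allocated group cannot restore one- and three-month readings that were never taken.

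**Working it through.** **Inputs.** Section 3.6 gives 90% versus 52.4%, power 80%, alpha 0.05, 22 per group, 20% dropout and 27 per group. The number never dilated, k, is not in the documents; I assume 1, 2 or 5 per arm. Five is about the whole dropout allowance (0.20 × 27 = 5.4). As a common true patency I use 52.4% and, by assumption, 75%; six-month values in Appendix 1 run from 53% to 90%.

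**1. The plan's own figure.** Two proportions, two-sided, pooled variance under the null, no continuity correction:

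n = [1.960 × √(2 × 0.712 × 0.288) + 0.842 × √(0.90 × 0.10 + 0.524 × 0.476)]² / 0.376² = (1.255 + 0.490)² / 0.1414 = 21.6, so 22 per group.

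22 × 1.2 = 26.4 gives 27; dividing instead, 22 / 0.8 = 27.5 gives 28. The stated 27 is close enough to use.

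**2. Following an undilated patient through the text.**

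- Section 3: did not undergo either procedure, so is in neither group as defined.
- Section 3.1: was allocated, so is in a randomised group.
- Synopsis endpoint: no fistuloplasty, so no start date for patency.
- Section 3.8: visits are listed without a start point; a schedule counted from the procedure has none for this patient.
- Section 3.5: applies if the patient is classed as withdrawn, and then asks only for the final visit, with no one- or three-month reading.
- Section 3.9: per protocol, so most naturally left out.

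No section states how this patient is followed or scored.

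**3. Effect of dropping k non-patent patients from one arm.** If p is patency among all 27, patency among those kept is p × 27/(27 − k), a rise of p × k/(27 − k).

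| k dropped | p = 52.4% | p = 75% |
|---|---|---|
| 1 | 52.4 × 1/26 = 2.0 points | 75 × 1/26 = 2.9 points |
| 2 | 52.4 × 2/25 = 4.2 points | 75 × 2/25 = 6.0 points |
| 5 | 52.4 × 5/22 = 11.9 points | 75 × 5/22 = 17.0 points |

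With no true difference and k lost from one arm only, the rise is a spurious difference in favour of the arm that lost them. With equal losses it cancels. With 5 lost in one arm and 2 in the other it is 7.7 points (64.3% − 56.6%) or 11.0 points (92.0% − 81.0%).

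**4. If the outcomes are simply unknown.** With 5 unobserved in each arm and the design rates among the other 22, the difference over all 27 runs from (19.8 − 11.528 − 5)/27 = 12.1 points to (19.8 + 5 − 11.528)/27 = 49.2 points, against a planned 37.6.

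**5. Power if undilated patients are kept and counted as not patent.** At 27 per arm and design rates among the dilated:

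| Undilated | Rates | Power |
|---|---|---|
| none | 90% v 52.4% | 88.5% |
| 2 per arm | 83.3% v 48.5% | 78.7% |
| 5 per arm | 73.3% v 42.7% | 63.2% |

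**The case against.** The best reply is that the section 3 wording is loose rather than binding. The synopsis and 3.1 also describe the groups by allocation: "patients will be randomized equally with a ratio 1:1 to ultrasound-guided fistuloplasty group and fluoroscopy-guided fistuloplasty group". Visits in 3.1 and 3.8 are not limited to dilated patients, 3.7 gives every subject six months of participation, and 3.5 brings withdrawn subjects to the final visit. On that reading an undilated patient is either still a subject or withdrawn, and either way may give a six-month reading. This stands in part. A reader might infer that the groups are defined solely by receipt of the procedure, or that undilated patients will have no outcome data at all; the documents do not support either. But the general wording does not clearly reach these patients, gives them no start date, and does not secure the one- and three-month readings.

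A second reply concerns direction. Because duplex is credited with finding stenosis "with 92% sensitivity and 84% specificity", a reader might infer that fistulograms will unmask false-positive entries, that those patients will leave the fluoroscopy arm, and that the bias favours fluoroscopy by a calculable amount. The documents do not support this:

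- No step cancels dilatation because of a fistulogram. Section 3.1 describes balloon inflation for both arms and uses fluoroscopy to judge technical success.
- The one imaging miss the protocol foresees is in the other arm, a stenosis not visible on ultrasound.
- A false-positive count needs an assumed prevalence. At 50% to 90%, the positive predictive value is 0.92p/(0.92p + 0.16(1 − p)) = 85.2% to 98.1%, or 4.0 to 0.5 of 27. Entry also requires a velocity ratio of at least 3, low flow and an abnormal thrill or pulse, so even that is only an upper guide.
- Turning the count into a patency bias would need false positives to fail if left alone yet do as well as everyone else if dilated, which is not coherent.

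A patient whose lesion could not be crossed may also be thought to have undergone the procedure and so count as a technical failure. That is possible, but the plan does not say so.

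The CONSORT flowchart was not available to this review. It may show patients allocated but not treated; if so, the text should be made to agree with it.

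**Conclusion.** The concern holds as a gap in the plan. Section 3 ties group membership and follow-up to receipt of the procedure, the endpoint clock starts at the procedure, and the only analysis is per protocol. Taken together, these leave out patients who were randomised but not dilated, with no secured follow-up at one, three and six months and no rule for scoring them. Some six-month data may still exist under the general wording.

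Loss could differ by arm, but the documents give no rate of non-dilatation, so neither the size nor the direction of any bias can be stated. The 2 to 3 points per dropped patient is an illustration. It assumes 27 per arm, that the dropped patient would have been non-patent, and a true patency between 52.4% and 75%. This should be corrected, since the change is small and missed visits cannot be recovered later.

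**What to change.** 1. Section 3: open both group definitions with *All patients randomised to* in place of the wording about having undergone the procedure.
2. Section 3.8: give every randomised patient the same visits from one start point for both arms, randomisation, and bring the synopsis endpoint into line. Record the procedure date so that waiting time can be reported by arm.
3. Keep every randomised patient in study follow-up and in the randomised comparison whatever theatre imaging shows. This governs data collection, not treatment.
4. State in advance how patency is scored when no dilatation takes place, and count failure to cross the lesion as technical failure.
5. Report the number not dilated, with reasons, by arm.
6. Section 3.9: pair this with an analysis by allocated group; without it the extra visits would not enter the comparison.

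The cost is a few sentences, a few routine visits and a slightly less favourable patency figure. Power falls if undilated patients count as not patent: from 88.5% with none to 78.7% with two per arm at the design rates. Starting at randomisation also means that a long wait for theatre brings the one-month reading closer to the procedure, which is a further reason to record the wait.
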